4. LENALIDOMIDE EDUCATION AND COUNSELING GUIDANCE DOCUMENT FOR MALE SUBJECTS

To be completed prior to each dispensing of lenalidomide.

Protocol Number: _____

Subject Name (Print): _____ DOB: ____ / ____ / ____ (dd/mmm/yyyy)

1. I have verified and counseled the subject regarding the following:

- Potential risk of fetal exposure to lenalidomide: A teratogenic potential of lenalidomide in humans cannot be ruled out. If lenalidomide is taken during pregnancy, it may cause birth defects or death to any unborn baby.
- The subject confirmed that he has practiced complete abstinence (True abstinence is acceptable when this is in line with the preferred and usual lifestyle of the subject. Periodic abstinence [eg calendar, ovulation, symptothermal or post-ovulation methods] and withdrawal are not acceptable methods of contraception.) or used a condom when engaging in sexual contact (including those who have had a vasectomy) with a pregnant female or FCBP, while taking lenalidomide, during dose interruptions and for at least 90 days after the last dose of lenalidomide.
- The subject confirmed that he has not impregnated his female partner while in the study.
- The subject confirmed that he will notify his study doctor if his female partner becomes pregnant and the female partner of a male subject taking lenalidomide confirmed that she will call her healthcare provider immediately if she becomes pregnant.
- The subject has not and will never share lenalidomide with anyone else.
- The subject confirmed that he has not donated and will not donate semen or sperm while taking lenalidomide or during dose interruptions and that he will not donate semen or sperm for at least 90 days after the last dose of lenalidomide.
- The subject has not and will not donate blood while taking lenalidomide, during dose interruptions and for at least 90 days after the last dose of lenalidomide.
- The subject has not and will not break, chew, or open lenalidomide capsules at any point.
- The subject confirmed that he will return unused lenalidomide capsules to the study doctor.

2. I have provided the Lenalidomide Information Sheet to the subject.

Do Not Dispense Lenalidomide if:

- The subject stated that he has or does not want to adhere to pregnancy precautions outlined within this PPP.

Counselor Name (Print): _____

Counselor Signature: _____ Date: ____ / ____ / ____ (dd/mmm/yyyy)

Maintain a copy of the Education and Counseling Guidance Document in the subject's records.

Appendix 9. Child-Pugh Score for Subjects with Liver Impairment

Measure	1 point	2 points	3 points
Total bilirubin, μ mol/L (mg/dL)	<34 (<2)	34-50 (2-3)	>50 (>3)
Serum albumin, g/L (g/dL)	>35 (>3.5)	28-35 (2.8-3.5)	<28 (<2.8)
PT/INR	<1.7	1.71-2.30	>2.30
Ascites	None	Mild	Moderate to Severe
Hepatic encephalopathy	None	Grade I-II (or suppressed with medication)	Grade III-IV (or refractory)

Points	Class
5-6	A
7-9	B
10-15	C

Source:

ORR	overall response rate
OS	overall survival
PCYC	Pharmacyclics Inc. (Sponsor)
PD	progressive disease
PFS	progression-free survival
PK	pharmacokinetic(s)
PO	per os (oral)
PR	partial response

Statistical Analysis Plan

PCYC-1123-CA

20APR2020

RP2D	Recommended Phase 2 Dose
SAE	serious adverse event
SAP	Statistical Analysis Plan
SD	stable disease
SPD	sum of the product of the diameters

1 INTRODUCTION

This statistical analysis plan (SAP) is based on Protocol Amendment 5, dated on 01JUN2016, and is to define key elements including variable definitions, and statistical methods for analysis of data in the evaluation of efficacy and safety of the study PCYC-1123-CA. Analyses of biomarker and pharmacokinetics data will be addressed in separate documents.

Analysis methods specified in this document take precedence over those described in the protocol, should there be any difference.

1.1 Study Design

This Phase 1b/2 study is designed to assess the safety and efficacy of ibrutinib in combination with lenalidomide and rituximab in subjects with relapsed/refractory diffuse large B-cell lymphoma (DLBCL) ineligible for a stem cell transplant. Phase 2 will evaluate only subjects with the non-GCB subtype of de novo DLBCL. Approximately 46 subjects will be enrolled in the Phase 1b portion. Phase 2 will enroll approximately 55 subjects to ensure enrollment of at least 49 response-evaluable subjects at 20 mg lenalidomide; approximately 28 additional subjects may be enrolled at 25 mg lenalidomide.

1.1.1 Phase 1b

In the dose escalation portion of the study, up to four cohorts may be explored, and the lenalidomide dose escalation will follow the 3+3+3 principle for the maximum tolerated dose (MTD) determination. Due to the fact that the subject population studied is significantly ill, and an inability to complete the dose-limiting toxicity (DLT) observation period may occur due to progression of disease, additional subjects may be screened and enrolled in each cohort. The DLT rules will continue to apply whereas if 1 DLT is observed, the cohort will be expanded to 6, and if 2 DLTs occur, the cohort will be expanded to 9.

Ibrutinib will be administered orally once daily at 560 mg and will be initiated on Day 1 of the first cycle. Treatment will be continuous (without interruption) and will continue until disease progression or unacceptable toxicity. Lenalidomide will be administered orally once daily at the dose designated by cohort on Days 1-21 of each 28-day cycle and will continue until disease progression or unacceptable toxicity. Rituximab 375 mg/m² will be administered intravenously (IV) on Day 1 of each 28-day (4-week) cycle for 6 cycles.

If 3 subjects in Cohort 1 experience a DLT, dose level -1 was planned to be enrolled (Table 1). After completion of Cohort 1, due to 3 DLTs in 7 evaluable subjects, a cohort at Dose Level -1 was opened. After completion of the Dose Level -1 cohort, if <33% of subjects experience a DLT, dose re-escalation to higher dose levels starting with the

lenalidomide dose of 15 mg may occur. If the dose level of 20 mg lenalidomide is determined to be safe and tolerated in the Phase 1b, this dose will be considered the recommended Phase 2 dose (RP2D), and a Phase 2 cohort with 20 mg lenalidomide will be initiated. Concurrent with the Phase 2 at 20 mg lenalidomide, a Phase 1b cohort with 25 mg lenalidomide may be initiated. If the interim analysis of the 20 mg lenalidomide cohort is negative, the 25 mg lenalidomide dose may be used in an additional cohort in the Phase 2, if safe and tolerated in the Phase 1b.

Table 1: Phase 1b Dose Levels

28-Day Dosing Cycle	Ibrutinib ^a	Lenalidomide ^b	Rituximab ^c
Dose Level -1^d	560 mg once daily	10 mg	375 mg/m ²
Dose Level 1 = starting dose (Cohort 1 & 1+)	560 mg once daily	15 mg	375 mg/m ²
Dose Level 2 (Cohort 2)	560 mg once daily	20 mg	375 mg/m ²
Dose Level 3 (Cohort 3)	560 mg once daily	25 mg	375 mg/m ²

a. Ibrutinib will be administered orally once daily beginning Cycle 1 Day 1
 b. Lenalidomide will be administered orally once daily on Days 1-21 of each 28-day cycle
 c. Rituximab will be administered IV on Day 1 of each 28-day cycle for 6 cycles
 d. If <33% of subjects experience a DLT at Dose Level -1, dose re-escalation to a higher dose level may occur.

At least 6 subjects will be treated at the MTD or in any cohort defined as the RP2D that supports the Phase 2.

1.1.2 Phase 2

The Phase 2 part of this study will be conducted as an international, multicenter, open-label study. Phase 2 will enroll approximately 49 response-evaluable subjects at 20 mg lenalidomide; approximately 28 additional subjects may be enrolled at 25 mg lenalidomide.

Eligible subjects will receive ibrutinib, lenalidomide and rituximab per the treatment schedule as shown below (Table 2). If determined to be safe and tolerated in the Phase 1b portion of the trial, the proposed dose of lenalidomide for Phase 2 is 20 mg. Subjects will be treated until disease progression or unacceptable toxicity.

Table 2: Treatment Schedule^a

	Cycles 1-6	Cycles 7+
Ibrutinib	PO daily	PO daily
Lenalidomide	PO daily Days 1-21	PO daily Days 1-21
Rituximab	IV on Day 1	NA

^a Each cycle will be 28-days in length (4 weeks) and subjects will continue until disease progression or unacceptable toxicity. Rituximab will be given for the first 6 cycles.

An interim analysis might be performed including approximately 28 evaluable subjects with adequate tumor response assessments. Details of the interim analysis and decision rules will be described in Section 1.5. In addition, if there are safety concerns, a cohort with ibrutinib and lenalidomide without rituximab may be considered in the Phase 2 part of the study.

Immunohistochemistry (IHC) and gene expression profiling (GEP) will be used to assess subject status with respect to the subtype of DLBCL. The limitations of IHC allow only a distinction between subjects as either non-germinal center B cell-like (non-GCB) or GCB phenotype, since within the non-GCB group, one may include subjects with a true unclassified (intermediate) subtype. With GEP, the subjects can be further categorized into the following subtypes: ABC, GCB, unclassified, and unknown due to tissue limitations. Throughout the protocol, the description of enrolled subjects as non-GCB is based on IHC testing used at screening; and the use of the term ABC subtype refers to subjects who have been subsequently profiled by GEP and then classified as the true ABC subtype.

1.2 Endpoints

1.2.1 Phase 1b

Primary Endpoints:

- MTD or RP2D
- Safety and tolerability of ibrutinib in combination with lenalidomide and rituximab in subjects with relapsed or refractory DLBCL

Secondary Endpoints:

- Overall response rate (ORR) and complete response (CR) rate

1.2.2 Phase 2

Primary Endpoint:

- ORR

Statistical Analysis Plan

PCYC-1123-CA

20APR2020

Secondary Endpoints:Efficacy:

- CR rate
- Duration of response (DOR)
- Progression-free survival (PFS)
- Overall survival (OS)

Safety:

- Frequency, severity, and relationship (to study drug) of AEs
- Frequency of AEs requiring discontinuation of study drug or dose reductions

Exploratory Analyses:

- Efficacy endpoints by DLBCL subtype per GEP
- Change in peripheral T/B/NK counts
- Change in serum immunoglobulin levels (IgG, IgM, and IgA)

1.3 Statistical Hypotheses

The main analysis for the Phase 2 part of this study will be the comparison of the response rate to the ORR of a historical control of 40%. The null hypothesis that the true ORR is 40% will be tested against a one-sided alternative that the ORR is 60%.

1.4 Sample Size Determination

The planned sample size for the Phase 2 part of this study is approximately 55 subjects to ensure enrollment of at least 49 response-evaluable subjects at 20 mg lenalidomide.

An interim analysis might be performed including approximately 28 evaluable subjects with adequate tumor response assessments. If only 11 or fewer responders ($\leq 11/28$) are observed, the Sponsor may consider discontinuation of the study; however, if there is evidence for clinical benefit from biomarker data or tumor measurements (showing clinically relevant tumor reductions, e.g. 40%, that fit the criteria for the response of SD), continued enrollment may be supported.

The main analysis will be the comparison of the response rate to the ORR of a historical control of 40%. The null hypothesis that the true ORR is 40% will be tested against a one-sided alternative that the ORR is 60%. The null hypothesis will be rejected if 27 or more responses are observed in the 49 subjects.

This design yields a 1-sided type I error rate of 0.025 and power of 80% when the true ORR is 60%. This statistical design including the number of subjects and the number of responders follows the statistical framework of Simon's minimax two-stage design (Simon 1989). Enrollment will continue while the interim analysis is being performed.

Approximately 28 additional subjects may be enrolled at 25 mg lenalidomide to explore the efficacy and safety at this higher dose of lenalidomide in Phase 2.

1.5 Planned Analyses

1.5.1 Timing of Analyses

An analysis will occur approximately 12 months after the last subject initiates study treatment or when all subjects have discontinued from the study treatment, whichever occurs first. A final analysis will occur 2 years after the last subject has been enrolled and will be reported in the CSR. The study completion is defined as 3 years from the last study treatment, the time point all subjects have exited the study due to any reason, or study termination at the Sponsor's discretion, whichever occurs first.

1.5.2 Interim Analysis

An interim analysis for Phase 2 at the 20 mg lenalidomide dose might be performed including approximately 28 evaluable subjects with adequate tumor response assessment. If only 11 or fewer responders ($\leq 11/28$) are observed, the Sponsor may consider discontinuation of the study; however, if there is evidence for clinical benefit from biomarker data or tumor measurements (showing clinically relevant tumor reductions, e.g. 40%, that fit the criteria for SD), continued enrollment may be supported.

At the interim analysis, the review committee could recommend:

- Continuation or discontinuation of the study with 20 mg lenalidomide; or
- Increase of the lenalidomide dose to 25 mg, if determined to be safe and tolerated in the Phase 1b, including approximately 28 evaluable subjects with adequate tumor response assessment followed by an interim analysis.

In addition, if there are safety concerns, a cohort with ibrutinib and lenalidomide without rituximab may be considered in the Phase 2. The decisions based on the interim analysis will be made by the Sponsor (at a minimum: the Medical Monitor or designee, a Drug Safety representative and a Biostatistician). Enrollment in the 20 mg lenalidomide cohort will continue while the interim analysis is being performed.

Statistical Analysis Plan

PCYC-1123-CA

20APR2020

1.6 Testing Procedure and Level of Significance

The null hypothesis that the true ORR is 40% will be tested at a 2-sided alpha of 0.05 for Part 2 at the 20 mg lenalidomide dose. If the lower bound of the 95% CI is greater than 40%, the study will be claimed as positive for Part 2 at the 20 mg lenalidomide dose.

1.7 Blinding and Randomization Methods (if applicable)

1.7.1 Blinding Method

This is an open-label study. Blinding does not apply.

1.7.2 Randomization Method

This is not a randomized study. Subjects are enrolled according to the order of Phase 1b to Phase 2 and low dose to high dose cohorts. Note: The Phase 2 was started at a 20 mg lenalidomide dose while the Phase 1b was still ongoing with a 25 mg lenalidomide cohort.

2 GENERAL ANALYSIS CONSIDERATION

The Phase 1b part of this study is a dose escalation study. All safety and efficacy assessments will be summarized by dose group. The Phase 2 part of this study is designed to assess the efficacy and safety of ibrutinib in combination with lenalidomide and rituximab in subjects with relapsed or refractory de novo non-GCB DLBCL.

In general, continuous variables will be summarized with descriptive statistics (mean, standard error or standard deviation, median, quartiles, minimum, and maximum). For categorical variables, the number and percentage of subjects in each applicable category will be provided. Time-to-event or duration-of-event endpoints will be based on the event and censoring dates.

All statistical analyses will be performed using SAS® version 9.3 or higher.

2.1 Analysis Sets

All-treated analysis population (Phase 1b/2)

The all-treated analysis population will include subjects who have been enrolled in the study and received any dose of study drug(s) in each study phase, respectively. This is the primary analysis population for all efficacy endpoints (i.e., PFS, OS), except ORR and the CR rate for the Phase 1b and Phase 2. This is also the sensitivity analysis population for ORR and CR.

Response-evaluable Population (Phase 1b/2)

Statistical Analysis Plan

PCYC-1123-CA

20APR2020

The response-evaluable population in the Phase 1b/2 study is defined as subjects in the all-treated population who have measurable disease at baseline and have at least 1 adequate post-treatment disease assessment by the investigator before the start of a subsequent anti-cancer therapy. This is the primary analysis population for ORR and the CR rate.

Safety Population (Phase 1b/2)

The safety population consists of all enrolled subjects who received at least one dose of study drug. The safety population will be used for the analysis of all safety and dosing data. For this study, this population is equivalent to the all-treated analysis population. They are interchangeably used.

2.2 Definitions of Subgroups

Analyses for the baseline subgroups (hereafter referred as “subgroup” or “subgroups”) will be performed for the selected primary and secondary endpoint variables analyses for Phases 1a and 2 except where noted in Table 3.

Table 3: Baseline Subgroups

Baseline Characteristics	Subgroup	Analysis Type
DLBCL subtype by GEP	ABC, GCB and Unclassified	E
DBLC subtype by IHC	GCB and Non-GCB	E
Transformed DLBCL (Phase 1b only)	Yes	E
Subjects with refractory disease	Yes	ORR and Baseline
Subjects with relapsed disease	Yes	ORR and Baseline
Subjects with primary refractory disease	Yes	ORR and Baseline

Analysis type: E = Efficacy (ORR, CR, PFS and OS).

3 SUBJECT INFORMATION

3.1 Subject disposition

Subject enrollment will be summarized by dose cohort in Phase 1b and in Phase 2, respectively. The disposition of all enrolled subjects will be summarized by study phase.

The disposition tables will include the following summaries.

- Analysis population (all-treated subjects)
- Enrollment by region, country and investigator
- Study treatment disposition and discontinuation
- Study status and the time on study

Statistical Analysis Plan

PCYC-1123-CA

20APR2020

The Kaplan-Meier estimates will be calculated to estimate the time on study using reversed censoring from the OS analysis.

3.2 Demographics and Baseline characteristics

Subject demographics (including age, sex, and race/ethnicity), general baseline characteristics (including ECOG performance status, weight and height), and baseline disease characteristics (including Ann Arbor staging, bulky disease, DLBCL category and number of prior therapies) will be summarized. Summary statistics will include means, standard deviations, and medians for continuous variables and proportions for categorical variables.

Concordance is summarized for the all-treated population between the DLBCL subtypes per GEP test by central lab and per IHC test by local lab.

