7.1.2. Confirm Eligibility

All necessary procedures and evaluations must be performed to document that the subject meets all of the inclusion criteria and none of the exclusion criteria ([Section 4](#)) including prior to the first dose on Day 1. Measurable disease documented by radiographic imaging is required at the time of study entry. Confirmation of non-GCB phenotype by IHC according to the central laboratory is required prior to enrollment to confirm eligibility for Phase 2 only.

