7.6.3. Gene Expression Profiling and Immunohistochemistry

Immunohistochemistry testing for determination of DLBCL subtype (GCB/non-GCB) will be performed at a central laboratory. DNA and RNA extracted from the tumor samples will be used for GEP and sequencing assays. An adequate amount of tissue must be available for both IHC and GEP to be eligible for the Phase 2 portion. Tumor tissue will also be required for the Phase 1b study to determine the DLBCL subtype. (Local laboratory results for DLBCL subtype for subjects in the Phase 1b may be collected). The sample can be archival tissue from original diagnosis, from relapsed or refractory disease or fresh in order to meet the requirement (see Laboratory Manual/Flow Chart for more details). These samples will be used for ABC/GCB/Type 3 DLBCL subtyping by GEP and may be used to identify biomarkers that may predict response or resistance to ibrutinib. Proteomic analyses to examine BCR-related signaling pathways or activation of BTK or related kinases may also be performed on remaining material from these samples.

The concordance of the central GEP and central IHC classifiers may be assessed with estimates of sensitivity and specificity of the IHC classifier given the central GEP subtype classification. The SAP will provide additional analysis details.

Tissue samples collected during the course of the study may be used for, but not limited to, biomarker assessments as noted above. In addition, samples collected from non-eligible subjects may be retained for purposes of validation of a diagnostic assay.

Refer to the Laboratory Manual/Flow Chart for detailed information on the required amount and acceptable preparations of sample and sample handling specifications and shipment to the central laboratory.

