10.3.8. Biomarkers

- Identification of signaling pathways or biomarkers that predict sensitivity or resistance to ibrutinib.
- Frequency of tumor mutations (or other molecular markers) between pre and post treatment tissue that predict acquired resistance.

The concordance of the central GEP and central IHC classifiers may be assessed with estimates of sensitivity and specificity of the IHC classifier given the central GEP subtype classification. The SAP will provide additional analysis details.

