Pregnancy Test (serum or urine) ^j		X	X	X	X	X	X ^j	X	X ^j	X	X	X	X	X ^j
T/B/NK Cell Count ^k		X			X	X		X		X	X ^k	X ^k	X ^k	X
Serum Immunoglobulins (Ig ^l) (Phase 2)						X					X ^l	X ^l	X ^l	X
Biomarker Blood Sample ^k		X				X	X	X		X	X ^k	X ^k	X ^k	X
PK Blood Sampling ^m (Phase 2)						X ^m	X ^m							
Radiologic Tumor Assessment														
CT Neck, Chest, Abdomen, Pelvis ⁿ		X						X		X	X ^{n,o}		X	
PET or PET/CT ⁿ		X									X ^{n,o}		X	
Other														
Survival Status ^p														X ^p
Subsequent Anticancer Therapy														X ^p

Abbreviations: C=cycle; CT=computed tomography; D=day; ECG=electrocardiogram; ECOG=Eastern Cooperative Oncology Group; EOT=End-of-Treatment Visit; LTFU=Long-Term Follow Up; RE=Response Evaluation; PD=progressive disease; PET=positron emission tomography; PO=oral; RFU=Response Follow Up

Footnotes for PCYC-1123-CA Schedule of Assessments:

^a CT/MRI and PET scans may be done per the Investigator's discretion during the response follow-up period.

^b Study Drug diary must be provided to the subjects at the beginning of each Day 1 visit to record daily dosing. Site personnel must instruct the subjects to bring the completed diary card with any used and unused study drugs at each study visit. Site personnel must reconcile and document the returned capsules from the subjects at each visit to ensure compliance.

^c **Phase 2 only:** A fresh tissue sample, archived unstained slides or an archived paraffin block must be sent to central lab for determination of DLBCL subtype by GEP and IHC using the Hans method **at Screening to confirm eligibility for enrollment.** For subjects in **Phase 1b**, available tissue (archived or fresh) will be sent to central lab at Screening for DLBCL subtyping. (Local laboratory results for DLBCL subtype for subjects in the Phase 1b may be collected). The tumor sample(s) can be archival tissue from original diagnosis, from relapsed or refractory disease, or a fresh (recent) biopsy, if done to confirm eligibility for this study.

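### SAP 3.2 compares GEP with local-laboratory IHC, although the protocol plans central IHC and Phase 2 enrolment was decided on central IHC

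*SAP*

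**What the plan says.** SAP section 3.2 contains one sentence on the subject. It has concordance of DLBCL subtype summarised in the all-treated population, "per GEP test by central lab and per IHC test by local lab". SAP section 1 gives the SAP priority over the protocol where methods differ, and SAP section 2.1 defines the all-treated population separately for each phase.

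The protocol describes a different comparison. Section 10.3.8 says: "The concordance of the central GEP and central IHC classifiers may be assessed with estimates of sensitivity and specificity of the IHC classifier", taking the central GEP subtype as reference. Section 7.6.3 repeats this, and both sections leave the details to the SAP.

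On who performs the IHC, section 7.6.3 says: "Immunohistochemistry testing for determination of DLBCL subtype (GCB/non-GCB) will be performed at a central laboratory". Footnote c of the Schedule of Assessments says that Phase 2 tissue "must be sent to central lab for determination of DLBCL subtype by GEP and IHC using the Hans method". Section 7.1.2 makes that result an entry condition: "Confirmation of non-GCB phenotype by IHC according to the central laboratory is required prior to enrollment to confirm eligibility for Phase 2 only". Local results appear in section 7.6.3, "Local laboratory results for DLBCL subtype for subjects in the Phase 1b may be collected", and in the same terms in footnote c.

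SAP section 6, on changes from the protocol's planned analyses, covers only the timing of the clinical study report.

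**The concern.** Central Hans IHC decided who entered Phase 2. Both documents acknowledge that an IHC non-GCB group can include cases that GEP would call unclassified, and efficacy by GEP subtype is an exploratory analysis. A reader will therefore want to know how many enrolled non-GCB subjects are ABC by GEP. A table built on local IHC does not answer that, and for Phase 2 the documents give no source for the local results.

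Correcting the laboratory leaves a second matter. Once central IHC is used, Phase 2 is a sample selected on the test being evaluated. The usual agreement and accuracy measures then reflect the selection, so the SAP needs to say which quantity Phase 2 can support.

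**Working it through.** The plan gives no figure to reproduce here. The check has two parts.

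**1. The texts side by side**

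| Item | Protocol | SAP |
|---|---|---|
| GEP source | Central (7.6.3, 10.3.8) | Central (3.2) |
| IHC source for concordance | Central (7.6.3, 10.3.8) | Local (3.2) |
| IHC used for Phase 2 entry | Central (7.1.2, footnote c) | IHC at screening, laboratory not named (1.1.2) |
| Local subtype results, Phase 1b | Optional (7.6.3, footnote c) | Required by 3.2 |
| Local subtype results, Phase 2 | Not mentioned | Required by 3.2 |
| Sensitivity and specificity | Optional (7.6.3, 10.3.8) | Not mentioned |
| Change declared | n/a | Not in section 6 |

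The SAP's priority clause settles which method governs. It does not supply data that the protocol does not plan to collect.

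**2. What Phase 2 can estimate with central IHC**

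Cross-classify treated Phase 2 subjects by central IHC and by GEP, taking ABC as the GEP-positive class for illustration:

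- a = IHC non-GCB and ABC
- b = IHC non-GCB and not ABC
- c = IHC GCB and ABC
- d = IHC GCB and not ABC

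Protocol 7.1.2 requires IHC non-GCB and exclusion criterion 1 removes GCB. The all-treated population holds no screen failures. So c = d = 0, apart from eligibility deviations. With n = a + b:

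- Sensitivity = a/(a + c) = a/a = 100%.
- Specificity = d/(b + d) = 0/b = 0%.
- Raw agreement = (a + d)/n = a/n.
- Chance agreement = (a/n)(1) + (b/n)(0) = a/n, so kappa = 0.

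Example with n = 55, the planned 20 mg enrolment, and an assumed 33 ABC: sensitivity 33/33, specificity 0/22, agreement 33/55 = 60%, chance agreement 60%, kappa (0.60 − 0.60)/(1 − 0.60) = 0.

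A simulation of 200,000 screened patients, with half assumed ABC, shows the same. True sensitivity/specificity pairs of 90/90, 70/70 and 50/50 (per cent) were recovered in the screened group. All three became 100/0 after selection on IHC non-GCB.

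The quantity that Phase 2 can estimate is P(ABC | IHC non-GCB) = a/n. The documents give no expected share, so a range is assumed, with Clopper-Pearson intervals at n = 55:

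| Assumed share | a | Exact 95% CI |
|---|---|---|
| 50% | 28 | 37% to 65% |
| 60% | 33 | 46% to 73% |
| 70% | 38 | 55% to 81% |
| 80% | 44 | 67% to 90% |

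Phase 1b is open to all DLBCL subtypes, so all four cells can be filled there, in at most about 46 subjects. If half were ABC (an assumption), each of sensitivity and specificity would rest on 23 subjects. At a true value of 80% the approximate half-width is 1.96 × √(0.8 × 0.2/23) = 1.96 × 0.083, or about 16 percentage points.

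**The case against.** The best counter-argument is that the sentence in SAP 3.2 is a modest baseline summary. It may be an additional table rather than a replacement: SAP section 1 sends biomarker analyses to separate documents, and the protocol lists central concordance under biomarkers. Those documents were not available, so a central comparison there cannot be ruled out. That limits the claim that the SAP has dropped the central comparison. It does not repair the wording of 3.2, and the protocol says that the SAP will give the details.

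A reader might also infer more than the documents support:

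- *That the SAP plans an invalid sensitivity and specificity.* It does not. It says only that concordance is summarised; the accuracy measures are optional protocol text.
- *That pooling the phases will distort the estimates.* No section plans a pooled accuracy estimate, and the all-treated population is defined by phase. SAP 3.2 is merely silent on layout.
- *That the table as written must show 100% and 0%.* That algebra holds for central IHC. A local result could read GCB in a subject who is non-GCB centrally, although the sample would still be selected on the central result.
- *That Phase 2 has no local IHC data.* This is inferred from silence. Nothing in the documents forbids collection, and the case report form and laboratory manual were not available.

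**Conclusion.** The point stands as a mismatch in the analysis specification. SAP 3.2 names an IHC source that differs from the protocol's, did not determine Phase 2 eligibility, has no collection planned for Phase 2 in the documents, and is not declared as a change. The number of Phase 2 subjects without a local result lies somewhere between none and all of about 55.

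The finding that Phase 2 cannot yield sensitivity or specificity rests on eligibility being applied as written and on central IHC being the test evaluated. It is a caution about the protocol's optional analysis, not an error in an analysis that the SAP commits to.

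The consequence is limited to a descriptive table. The primary ORR test, the secondary endpoints, the interim rule and the safety analyses do not use it, and it cannot alter who was enrolled.

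**What to change.** 1. In SAP 3.2, change the IHC source from local to central laboratory and present concordance separately for Phase 1b and Phase 2. Show any local IHC results as a Phase 1b listing. If local IHC was intended, say so in section 6, with the reason and the number of subjects who have it in each phase.
2. For Phase 2, report the GEP distribution (ABC, unclassified, GCB) among central-IHC non-GCB subjects, and the proportion ABC with its exact 95% CI. State how many subjects have an unknown GEP result and whether they are in the denominator.
3. If sensitivity and specificity are estimated, restrict them to Phase 1b. Define the GEP-positive class beforehand (ABC alone, or ABC plus unclassified), give exact intervals, and acknowledge the imprecision from at most about 46 subjects.

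The cost is a few lines of SAP text and one revised table. The protocol already requires central IHC and GEP tissue in Phase 2 and sends available Phase 1b tissue to the central laboratory, so no new data are needed.
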